10.1.3 Recruitment Strategy

Subjects may be recruited through several sources, including but not limited to the site database and advertising in traditional or online media.

10.1.4 Confidentiality

All information generated in this trial will be considered confidential and will not be disclosed to anyone not directly concerned with the trial without the sponsor's prior written permission. Subject confidentiality requirements of the region(s) where the trial is conducted will be met. However, authorized regulatory officials and sponsor personnel (or their representatives) may be allowed full access to inspect and copy the records, consistent with local requirements. All trial devices and/or other materials collected shall be used solely in accordance with this protocol, unless otherwise agreed to in writing by the sponsor.

Subjects will be identified only by unique subject ID in the eCRF. If further subject identification is required, subjects' full names may be made known to a regulatory agency or other authorized officials, if necessary, subject to local regulations.

10.1.5 Quality Control and Quality Assurance

10.1.5.1 Monitoring

The sponsor has ethical, legal, and scientific obligations to follow this trial in accordance with established research principles, the applicable ICH GCP guidance, and applicable regulatory requirements and local laws. As part of a concerted effort to fulfill these obligations (maintain current personal knowledge of the progress of the trial), the sponsor's monitors will visit the site during the trial, as well as communicate frequently via telephone, email, and written communications. In addition, all investigators and trial site personnel will undergo initial and ongoing training for this particular trial, and this training will be clearly documented.

Confidential - Proprietary Information

43

10.1.5.2 Auditing

The sponsor's Quality Assurance Unit (or representative) may conduct trial site audits. Audits will include, but are not limited to, investigational device supply, presence of required documents, the informed consent process, site operations, delegation of authority and training, and a review of the eCRF with source documents, as applicable. The investigator will agree to cooperate and participate with audits.

Regulatory authorities may inspect the investigator site during or after the trial. The investigator will cooperate with such inspections and will contact the sponsor immediately if such an inspection occurs.

10.1.6 Protocol Deviations

In the event of a significant/major deviation from the protocol due to an emergency, accident, or mistake (eg, violation of informed consent process, trial device dispensing or subject dosing error, subject enrolled in violation of eligibility criteria or concomitant medication criteria), the investigator or designee will contact the sponsor or designee at the earliest possible time by telephone or via email. The investigator and sponsor (or designee) will come as quickly as possible to a joint decision regarding the subject's continuation in the trial. This decision will be documented by the investigator and the sponsor (or designee) and reviewed by the site monitor.

Any major protocol deviation will be recorded in the eCRF along with the start date and details of the deviation.

10.1.7 Records Management

10.1.7.1 Source Documents

Source documents are defined as the results of original observations and activities of a clinical investigation. Source documents will include but are not limited to medical records, electronic data, screening logs, progress notes, paper-based assessments and scales, and recorded data from automated instruments or applications. All source documents pertaining to this trial will be maintained by the investigators and made available for direct inspection by authorized persons.

Investigator(s)/institution(s) will permit trial-related monitoring, audits, IRB review, and regulatory inspection(s) by providing direct access to source data/documents by authorized persons as defined in the ICF. In all cases, subject confidentiality must be maintained in accordance with local regulatory requirements.

Confidential - Proprietary Information

44

10.1.7.2 Data Collection

During each subject's visit to the site, an investigator or their designee participating in the trial will record information to document all significant observations. At a minimum, these notes will contain:

- Documentation of the informed consent process, including any revised ICFs;
- Documentation of the investigator's decision to enroll the subject into the trial, the review of all inclusion/exclusion criteria prior to initiation of any trial procedures, and confirmation of the subject's actual participation in the trial;
- Documentation of baseline and demographic characteristics (eg, age, sex at birth, race, ethnicity);
- The date of the visit and the corresponding Visit or Day in the trial schedule;
- General subject status remarks, including any *significant* medical findings. The severity, frequency, duration, action taken, and outcome of any AEs and the investigator's assessment of relationship to trial investigational device must also be recorded;
- Any changes in concomitant medications or dosages;
- A general reference to the procedures completed, including dosing and trial procedure compliance;
- The signature (or initials) and date of the investigator (or designee) who made an entry in the medical record.

In addition, any contact with the subject via telephone or other means that provides significant clinical information will also be documented in the progress notes as described above.

Information from medical records and other source documents will be entered by investigative site personnel onto eCRFs in the sponsor's electronic data capture (EDC) system that is 21 Code of Federal Regulations (CFR) Part 11 compliant. Changes to the data will be captured by an automatic audit trail in the EDC system.

At the end of the trial, the investigator must certify that the data entered into the eCRF application are complete and accurate. After database lock, the investigator will receive an electronic copy of the subject data.

10.1.7.3 File Management at the Trial Site

The investigator will ensure that the trial site file is maintained in accordance with applicable ICH GCP guidance and as required by applicable local regulations. The investigator/institution will take measures to prevent accidental or premature destruction of these documents.

45

10.1.7.4 Records Retention at the Trial Site

The FDA regulations require all investigators participating in clinical drug studies to maintain detailed clinical data for one of the following periods:

- A period of at least 2 years after the date on which a New Drug Application is approved by the FDA;
- A period of 2 years after the sponsor has notified the FDA that investigation with this drug is discontinued.

The investigator must not dispose of any records relevant to this trial without either (1) written permission from the sponsor or (2) provision of an opportunity for the sponsor to collect such records. The investigator will be responsible to maintain adequate and accurate electronic or hard copy source documents of all observations and data generated during this trial including any data clarification forms received from the sponsor. Such documentation is subject to inspection by the sponsor and relevant regulatory authorities. If the investigator withdraws from the trial (eg, due to relocation or retirement), all trial-related records should be transferred to a mutually agreed-upon designee within a sponsor-specified timeframe. Notice of such transfer will be given to the sponsor in writing.

10.1.7.5 Dissemination of Clinical Trial Data

Not applicable.

10.1.7.6 Publication Authorship Requirements

Authorship for any Otsuka-sponsored publications resulting from the conduct of this trial will be based on International Committee of Medical Journal Editors (ICMJE) authorship criteria (http://www.icmje.org/recommendations). According to ICMJE guidelines, one may be considered an author only if the following criteria are met:

- 1) Substantial contributions to the conception or design of the work; or the acquisition, analysis, or interpretation of data for the work; AND
- 2) Drafting the work or revising it critically for important intellectual content; AND
- 3) Final approval of the version to be published; AND
- 4) Agreement to be accountable for all aspects of the work in ensuring that questions related to the accuracy or integrity of any part of the work are appropriately investigated and resolved.

All authors must meet the above criteria, and all who qualify for authorship based on the above criteria should be listed as authors.

Investigators or other personnel involved in the conduct of the trial who do not qualify for authorship may be acknowledged in publications resulting from the trial. By agreeing

Confidential - Proprietary Information

46

to participate in the trial, investigators or other personnel involved in the conduct of the trial consent to such acknowledgement in any publications resulting from its conduct.

Confidential - Proprietary Information

10.2 Appendix 2: Contraceptive Guidance and Collection of Pregnancy Information

Females of childbearing potential (FOCBP) are females whose menstruation has started and who are not documented as sterile (eg, have had a bilateral oophorectomy, or hysterectomy, or who have been postmenopausal for at least 12 months). Females of non-childbearing potential do not meet definition of FOCBP.

Any subject that is currently pregnant or planning to become pregnant at the time of trial start is not eligible for participation. Females of childbearing potential are required to have a negative urine pregnancy test during screening. Subjects prescribed and taking aripiprazole should consult with their prescribing physicians regarding contraceptive recommendations with respect to family planning.

48

10.3 Appendix 3: Protocol Amendments

The investigator will not make any changes to this protocol without the sponsor's prior written consent and subsequent approval/favorable opinion by the IRB. Any permanent change to the protocol, whether an overall change or a change for specific trial site(s), must be handled as a protocol amendment. Any amendment will be written by the sponsor. Each amendment will be submitted to the IRB, as required by local regulations. Except for "administrative" or "non-substantial" amendments, investigators will wait for IRB approval/favorable opinion of the amended protocol before implementing the change(s). Non-substantial amendments are defined as having no effect on the safety of subjects, conduct or management of the trial, trial design, or the quality or safety of intervention(s) used in the trial. A protocol change intended to eliminate an apparent immediate hazard to subjects should be implemented immediately after agreement by the sponsor and investigator, followed by IRB notification within local applicable timelines.

When the IRB, investigators, and/or the sponsor conclude that the protocol amendment substantially alters the trial design and/or increases the potential risk to the subject, the currently approved written ICF will require similar modification. In such cases, after approval/favorable opinion of the new ICF by the IRB, repeat written informed consent will be obtained from currently enrolled subjects in the trial before the amendment-specified changes in the trial are implemented.

4.0 Purpose

The Statistical Analysis Plan (SAP) describes the statistical methods to be used during the reporting and analyses of data collected under Otsuka Pharmaceutical Development & Commercialization, Inc's Protocol 031-201-00521 dated 18-APR-2023.

5.0 Scope

The Statistical Analysis Plan outlines the following:

- Study Objectives
- Study Design
- Applicable Study Definitions
- Statistical Methods

6.0 Introduction

This SAP should be read in conjunction with the study protocol and case report form (CRF). Any further changes to the protocol or CRF may necessitate updates to the SAP.

6.1 Changes from Protocol

There are no major discrepancies between protocol and SAP, only the following minor differences are described:

- 1. Population definitions (SCR, FAS, FAS-Cohort 1, and FAS-Cohort 2) added, the protocol specified the intent-to-treat population, however, the full analysis set will be used.
- 2. The unanticipated adverse device effects stated in the protocol removed from the analysis.
- 3. AEs leading to discontinuation of the investigational device removed from analysis, instead AEs leading to study discontinuation will be analyzed.

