2.3.1.2 Allergic Reaction

An allergic reaction could potentially arise from exposure to components of the patch adhesive.

To mitigate the risk of this potential hazard, prospective subjects who have a known allergy to skin adhesives will be excluded from the trial. Allergy to bandages, tapes, and latex will be specifically queried.

Subjects will be told that they are free to remove the patches at any time and to inform the clinical research site immediately. Subjects will also be told to reach out for emergency medical care should they have immediate need for medical attention.

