4.5 Definition of Completed Subjects

The trial period is defined as the time period during which subjects are evaluated for the primary objective of the trial irrespective of whether or not the subject wears the patch or ingests all IEMs. Subjects who are evaluated at the last scheduled visit will be defined as trial completers.

5 Trial Population

Two cohorts of subjects will be enrolled in this trial.

Cohort 1: A minimum of 24 healthy subjects will be tested to obtain a minimum of 360 miniature IEM tablet ingestions for Cohort 1. Healthy subjects will be drawn from nonvulnerable subpopulations. If a subject fails to complete participation in the testing, for whatever reason, a new, qualified candidate may be enrolled as a replacement.

Cohort 2: A minimum of 30 subjects with SMI will be tested to obtain a minimum of 30 Abilify MyCite ingestions for Cohort 2. Subjects will ingest Abilify MyCite at the same dose as their currently prescribed aripiprazole. If a subject fails to complete

Confidential - Proprietary Information

participation in the testing, for whatever reason, a new, qualified candidate may be enrolled as a replacement.

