7.3 Discontinuation of Trial Device

Under certain circumstances, it may be necessary for a subject to permanently discontinue the trial. If trial IEMs or patches are permanently discontinued, the subject should, if at all possible, remain in the trial to be evaluated for safety assessments. See the schedule of assessments (SoA) for data to be collected at the time of discontinuation of trial device and follow-up and for any further evaluations that need to be completed. If a subject discontinues the trial due to an AE, the investigator, or other trial personnel, will make every effort to follow the event until it has resolved or stabilized.

For each subject who discontinues the trial, the main reason for discontinuation will be recorded in the eCRF (refer to Section 7.4.1).

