9.4.2 Secondary Endpoint

The frequency and severity of AEs, device-related AEs, SAEs, AEs leading to discontinuation, and unanticipated adverse device effects will be summarized.

9.4.2.1 **Adverse Events**

All AEs will be coded by system organ class and Medical Dictionary for Regulatory Activities (MedDRA) preferred term. The incidence of the following events will be summarized:

- AEs
- AEs by severity •
- AEs potentially causally related to the investigational device
- AEs with an outcome of death •
- **SAEs** •
- AEs leading to discontinuation of the investigational device

9.4.2.2 **Clinical Laboratory Data**

Not applicable.

9.4.2.3 **Physical Examination and Vital Signs Data**

Baseline vital signs data will be provided in a listing.

9.4.2.4 **Electrocardiogram Data**

Not applicable.

Confidential - Proprietary Information

40

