12.6.1 Treatment-Emergent Adverse Events

All AEs reported in the CRF will be coded using MedDRA.

An overall summary of TEAEs, including the number of events reported, and the number and percentage of subjects will be prepared by cohort in a table, as specified below:

- Subjects reporting at least 1 TEAE
- Subjects reporting at least 1 serious TEAE
- Subjects reporting at least 1 device/patch related TEAE
- Subjects reporting at least 1 device/patch related TEAE (by skin irritation score from 0-7)

CCI

Page 17 of 20

Strictly Confidential. © 2023, PRA Health Sciences. All rights reserved.

- Subjects reporting at least 1 clinically significant TEAE (defined by skin irritation score ≥ 2)
- Subjects reporting at least 1 Abilify MyCite treatment related TEAE (Cohort 2 only)
- Subject reported receiving at least 1 TEAE with concomitant or additional therapy
- Subjects with any TEAE leading to death
- Subjects discontinuing the study due to a TEAE
- Subjects discontinuing the study due to a device/patch related TEAE
- Subjects discontinuing the study due to an Abilify MyCite treatment related TEAE

Furthermore, a breakdown of the number and percentage of subjects reporting TEAE, categorized by system organ class (SOC) and preferred term (PT) coded according to the MedDRA dictionary (Version 26.0), will be presented. Note that counting will be by subject not event and subjects are only counted once within each SOC or PT. Therefore, when counting the number of subjects with each event, subjects with multiple events within a particular SOC or PT will be counted under the category of their most severe event within that SOC or PT. The list of TEAE tables is the following:

- TEAEs by SOC and PT
- Clinically significant TEAEs (defined as device/patch related TEAE and skin irritation score ≥ 2) by SOC and PT
- Any TEAE by maximum severity (mild, moderate, severe) by SOC and PT
- Any TEAE related to study device/patch by SOC and PT
- Any TEAE related to Abilify MyCite treatment by SOC and PT (Cohort 2 only)
- Serious TEAEs by SOC and PT
- TEAE leading to death by SOC and PT
- TEAEs leading to study discontinuation by SOC and PT

All AEs recorded on the CRF will be listed with MedDRA SOC and PT. The TEAEs will be marked with a flag within the listing. A footnote will state if no AE occurred after screening and before the subject wore any patches or took any tablet.

Independent listings will be provided with MedDRA SOC and PT for:

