- Device/Patch related TEAEs (with skin irritation score evaluation),
- Abilify MyCite treatment related TEAEs (Cohort 2 only),
- TEAEs leading to study discontinuation

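### The SAP counts AEs that end trial participation instead of AEs that end device use, so a subject who stops the patch for an AE but stays in the trial is in no AE discontinuation output

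*SAP*

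**What the plan says.** The AE section of the protocol's statistical plan (9.4.2.1) lists the incidences to be summarised. One of them is "AEs leading to discontinuation of the investigational device".

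SAP 6.1 presents its departures from the protocol as minor. Item 3 reads: "AEs leading to discontinuation of the investigational device removed from analysis, instead AEs leading to study discontinuation will be analyzed". No reason is given.

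SAP 12.6.1 carries this through. Its overall TEAE summary has three discontinuation rows, all about leaving the study: for any TEAE, for a patch-related one ("Subjects discontinuing the study due to a device/patch related TEAE"), and for one related to Abilify MyCite. There is one discontinuation table by SOC and PT and one discontinuation listing ("TEAEs leading to study discontinuation"), both also at study level.

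The SAP also says "All AEs recorded on the CRF will be listed with MedDRA SOC and PT". It does not specify the other columns of that listing.

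**The concern.** Stopping the device and leaving the trial are different events, and this protocol keeps them apart. It expects skin irritation from wear (2.3.1.1), leaves subjects free to take the patch off, and asks those who stop to remain for safety follow-up. The more closely a site follows that request, the fewer AE-driven patch stops appear in the SAP's replacement output.

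The only secondary objective is to characterise AEs associated with the device. For an adhesive patch worn for about a week, whether an AE ended wear is a natural tolerability result, and the protocol planned to report it. Under the SAP, two subjects with the same skin score look alike in every summary row, even if one wore the patch to Day 8 and the other took it off early because of the reaction.

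**Working it through.** The plan states no figure to reproduce. The check sets the protocol's rules beside the SAP's outputs.

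**1. Can a subject stop the patch for an AE and still complete the trial?**

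- Protocol 2.3.1.2: "Subjects will be told that they are free to remove the patches at any time and to inform the clinical research site immediately".
- Protocol 7.3: "If trial IEMs or patches are permanently discontinued, the subject should, if at all possible, remain in the trial to be evaluated for safety assessments".
- Protocol 4.5: "Subjects who are evaluated at the last scheduled visit will be defined as trial completers". The same section defines the trial period without regard to whether the patch is worn.

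Together these allow it.

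**2. Which SAP outputs would count such a subject?** Take a subject who removes the patch on Day 3 because of a skin reaction and attends Visit 3.

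| SAP output | What it shows for this subject |
|---|---|
| 12.6.1 overall, SOC/PT, severity and patch-related tables | Event counted |
| 12.6.1 skin-score rows | Event graded; not whether it ended wear |
| 12.6.1 discontinuation: 3 rows, 1 table, 1 listing | Not counted |
| 12.1 disposition | Study completer |
| 12.3.1 and 12.3.2 ingestion outputs | Day 1 tablets taken; nothing on later removal |
| 12.3.3 patch listing | A removal date, without a reason |
| All-AE listing and patch-related TEAE listing | Event listed; action taken not specified as a column |

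Count of AE discontinuation outputs: 3 + 1 + 1 = 5. Trial level: 5. Device level: 0.

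**3. Does the patch listing in SAP 12.3.3 close the gap?** Only in part.

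- It asks for a reason when removal was not completed, not when removal was early.
- Its date field holds patches taken off and patches that fell off, without separating them. It also holds self-removals on Day 8 when the clinic visit is late, which Protocol 8 (Follow-up Visit) instructs.
- It is based on the FAS, which requires at least one tablet. The safety set also admits a subject who wore a patch, took no tablet and had a safety assessment.

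**4. Are the data likely to exist?** Protocol 7.3 requires a recorded reason for leaving the trial, and 7.3.1 one for interrupting device use. Neither expressly requires a reason for a permanent patch stop in a subject who stays. SAP 10.5 uses discontinuation or interruption of the investigational product when classifying AEs that began before patch or tablet. That suggests a CRF field of this kind but does not prove it.

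**5. Size per subject.** At the planned minimums, 1/24 = 4.2% in Cohort 1 and 1/30 = 3.3% in Cohort 2. These show only how much one uncounted subject weighs. They do not estimate how many there would be.

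**The case against.** The case on the other side has five parts.

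- **The endpoint wording is open.** The synopsis, Protocol Table 3-1 and the lead sentence of 9.4.2 name AEs leading to discontinuation without saying of what. Only the 9.4.2.1 bullet specifies the device. SAP 9.1 keeps the open wording, and 6.1 discloses how it is settled. This stands: a reader might infer that a named secondary endpoint has been deleted, and the documents do not support that. What is dropped is one specified summary under the endpoint.
- **The two events overlap.** Protocol 7.4.1 places undue risk from continuing the device or tablets under the AE reason for leaving the trial. Protocol 6.4 withdraws non-compliant subjects, and SAP 12.1 has a matching reason for device or patch non-compliance. Some AE-driven device stops will therefore be recorded as trial discontinuations. This stands and narrows the gap. It does not close it, because 7.3 asks subjects who stop the device to stay where possible.
- **The information can be pieced together.** With minimums of 24 and 30 subjects, AE dates can be matched by subject to removal dates. This stands in part: the match is an inference, and fall-offs and Day 8 self-removals blur it.
- **The CRF is unseen.** The SAP is to be read with it. Whether the link is collected, and how cheaply it can be shown, cannot be settled here. This stands and limits the fix.
- **The stakes are modest.** SAP 8.1 calls the study exploratory, and the output is descriptive. This stands and makes the point an inexpensive improvement rather than a flaw in the main analysis.

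**Conclusion.** The point holds in a limited form. The SAP's replacement does not measure what Protocol 9.4.2.1 planned, and a subject who stops the patch for an AE but stays in the trial is absent from every AE discontinuation output. PDA, the latency measures and the sample size are not affected.

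No number of affected subjects can be given, because the documents state no rate of early removal. The conclusion rests on two assumptions: that SAP 12.1, 12.3 and 12.6 list all planned outputs, and that the AE listing will not show action taken, which the SAP leaves open.

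Three stronger readings are tempting and not supported:

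- **That safety data are lost.** Every TEAE stays in the tables and listings, and patch-related ones carry a skin score.
- **That all AE-driven patch stops disappear.** Some become trial withdrawals, and stops during Day 1 dosing are partly visible in the ingestion outputs.
- **That most cases are missed because dosing fills only a small part of the wear period.** A share of wear time is not a share of events, since removals need not be spread evenly over time.

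The removal of unanticipated adverse device effects in SAP 6.1 item 2 is a separate, disclosed matter and adds no weight here.

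**What to change.** 1. In SAP 12.6.1 add, by cohort, one summary row and one listing of TEAEs that led to permanent discontinuation of the patch or tablets. Keep the study-level rows beside them.
2. In SAP 9.1 state that discontinuation covers both device and study, and amend item 3 of 6.1 to match.
3. Identify cases from the AE action-taken field or a device-stop reason, not from the removal date alone. Confirm first that the CRF holds one of these.
4. If it holds neither, give that as the reason for the change in SAP 6.1. Then present AE dates beside patch-removal dates by subject in one listing, with a note that the removal dates include fall-offs and Day 8 self-removals.

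The cost is one row and one listing per cohort, with no new subject procedures, provided the field exists. Without it, the cost is one sentence in 6.1 and one combined listing. Querying site notes for action taken would be more than an SAP edit and is not proposed.
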